14.1.9 Suspected Unexpected Serious Adverse Reaction

AEs that meet the criteria of serious, related to study drug, and unexpected per investigator brochure, qualify for expedited reporting to the regulatory authorities. The site Investigator will assess all SAE's occurring at his/her site and evaluate for "unexpectedness" and relationship to study drug. The site Investigator is required to complete and submit a voluntary MedWatch Report for events deemed, as serious, study drug related and unexpected at:

https://www.accessdata.fda.gov/scripts/medwatch/.

A copy of this report should be kept at the site.

14.1.10 Pregnancy

Pregnancy occurring during a clinical investigation, although not considered a serious adverse event, must be reported within the same timelines as a serious adverse event. The pregnancy will be recorded on the appropriate paper pregnancy tracking form. The pregnancy will be followed until final outcome. Any associated AEs or SAEs that occur to the mother or fetus will be recorded in the AE eCRF, within the EDC system.

15 STATISTICAL METHODS AND DATA ANALYSIS

15.1 General Design Issues

All planned analyses will be prospectively defined for this study and approved by the CC. The statistical analysis plan (SAP) will contain detailed information regarding the data analysis. The SAP will be finalized prior to trial completion and will be approved by the coordinating center statistical team.

Analysis of the DOAC LVAD Study will be based on intention to treat (ITT). That is, participants will be analyzed (and endpoints attributed) according to the treatment strategy to which participants are randomized, regardless of subsequent additional post-randomization treatment and medical care. The ITT population will correspond to all randomized participants. The primary and secondary analyses will follow the ITT principle.

Baseline demographic and clinical variables will be summarized for each randomized arm of the study. Descriptive summaries of the distribution of continuous variables will be presented in terms of percentiles (e.g., median, 25th and 75th percentiles) along with means and standard deviations. Categorical variables will be summarized in terms of frequencies and percentages.

In addition, exploratory analyses will be performed to help explain and understand findings observed from the planned analyses. Statistical tests with a p-value <0.05 will be considered statistically significant, unless otherwise stated. Analyses will be performed using SAS software (SAS Institute, Inc, Cary, NC).

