12.2 Secondary Endpoints

- 1. Survival free of any stroke
- 2. Survival free of ischemic stroke
- 3. Survival free of hemorrhagic stroke
- 4. Survival free of device thrombosis
- 5. Survival free of aortic root thrombus
- 6. Survival free of gastrointestinal bleeding
- 7. Survival free of major non-gastrointestinal bleeding
- 8. All-cause mortality
- 9. Cardiovascular mortality

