15.2 Sample Size Justification and Randomization

Participants will be randomized in a 1:1 allocation ratio using a permuted block design with stratification based on the time from LVAD implant (<3 months or ≥3 months). The number of patients ≥3 months from LVAD implant will be capped at 20 participants. As this is an initial pilot study to assess safety and feasibility, we plan to enroll 40 patients.

For the primary purposes of this pilot study, each patient's data will be reviewed individually. Patients newly implanted vs previously implanted with a HM3 LVAD may be analyzed as distinct subgroups. The sample size of up to forty (40) implanted patients is based upon industry standards for early-stage studies of medical devices; the sample size was not statistically derived. This study is not designed to provide statistical significance of the outcomes. The study will provide data to be used for subsequent design and development of the phase III clinical trials. An interim report may be generated prior to completion of enrollment for regulatory or publication purposes.

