15.3 Analysis of the Primary Endpoint

For the primary endpoint, a time-to-event analysis will be conducted. The Cox regression model for survival data will be used to test the statistical significance of differences in the composite endpoint (survival free of major hemocompatibility related adverse event) between the two treatment groups. Certain clinical covariates may be used in the regression model (age, sex, race, atrial fibrillation, history of stroke or bleeding prior to LVAD, early (<3 months) or late (≥3 months) after implant, laboratory parameters, hemodynamics, coagulation marker measures).

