15.4 Analysis of Secondary and Tertiary Endpoints

The key secondary endpoint will be analyzed for time-to-event endpoints, using the Cox regression model for survival data will be used to test the statistical significance of differences in mortality between the treatments. Kaplan-Meier curves will be generated to graphically display the mortality rates as a function of time from randomization in each treatment. Patients will be censored when upgraded to a status 1-3, at the time of transplant, transfer of care to another LVAD center, device decommissioning or explant for myocardial recovery.

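### The secondary endpoints fall under a p<0.05 significance rule that the sample size section disowns, with no testing order and a key secondary endpoint that is never identified

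*Combined protocol and SAP*

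**What the plan says.** **The significance rule.** Section 15.1 applies one default to the whole analysis: "Statistical tests with a p-value <0.05 will be considered statistically significant, unless otherwise stated". Nothing later in the document states otherwise for a secondary endpoint. The same section uses the word exploratory only for extra analyses meant to explain the planned ones.

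**The endpoints.** Sections 4.2 and 12.2 each list nine secondary endpoints. Seven are survival-free-of-event endpoints, such as "Survival free of major non-gastrointestinal bleeding". The other two are all-cause mortality and "9. Cardiovascular mortality". They are numbered, but the numbering is not described as a testing order. (The executive summary lists eight, without aortic root thrombus.)

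**The secondary analysis.** Section 15.4 opens with "The key secondary endpoint will be analyzed for time-to-event endpoints, using the Cox regression model for survival data" and goes on to say that this model will be "used to test the statistical significance of differences in mortality between the treatments". It does not say which endpoint is key.

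**The disclaimer.** Section 15.2 describes an initial pilot whose sample size has no statistical derivation, and adds: "This study is not designed to provide statistical significance of the outcomes".

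**The concern.** A reader can follow 15.1 and 15.4 and label any secondary result below 0.05 as significant, or follow 15.2 and label none. The plan does not settle which.

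This matters for two reasons. First, with several endpoints, no testing order and no division of alpha, a chance difference in stroke, thrombosis, bleeding or death may be reported as significant. Section 15.2 says the data will feed phase III design and allows an interim report for regulatory or publication use, so such a label could carry weight.

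Second, the key secondary endpoint is open. Section 15.4 points to mortality, and 12.2 has two mortality endpoints that can give different answers. The trial is open label and 15.1 requires the SAP only before trial completion, so the choice could be made after outcomes are known.

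**Working it through.** The documents give no family-wise error rate, power or event count, so there is no figure of the plan's own to reproduce. The question is what the 0.05 rule would imply if applied to all nine endpoints.

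**Inputs from the document**
- Per-test level 0.05 (15.1). Sidedness is not stated; two-sided is assumed because 15.3 and 15.4 speak of differences.
- Nine secondary endpoints (12.2).
- 40 patients, 1:1, so about 20 per arm (15.2); 24 weeks (9.1).
- A Cox model (15.4), without saying whether the p-value is from a score, Wald or likelihood-ratio test.
- GI bleeding in up to 25% of patients in the first year (section 5). At a constant hazard this is 1 − 0.75^(24/52) = 12% by 24 weeks. Section 5 says these bleeds cluster in the first 3 months, so a higher figure is possible.

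**Inputs that are assumed** (24-week risks, same in both arms; low / middle / high)
- Ischemic stroke 3 / 5 / 8%; hemorrhagic stroke 2 / 3 / 5%
- Device thrombosis 1 / 3 / 5%; aortic root thrombus 1 / 3 / 5%
- GI bleeding 12 / 15 / 25%; major non-GI bleeding 8 / 15 / 25%
- Cardiovascular death 3 / 5 / 8%; other death 2 / 3 / 5%

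**Step 1: reference values.** Nine independent tests would give 1 − 0.95^9 = 37.0%. That is too high here, because death enters seven of the endpoints as a component and the stroke endpoints are nested. With nine equally correlated normal statistics the figure is 32.6% at correlation 0.3, 27.0% at 0.5, 20.2% at 0.7 and 12.4% at 0.9. The documents give no correlation.

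**Step 2: simulate the nine endpoints.** Exponential event times with shared deaths, 20 per arm, no true difference. The score test uses Z = (O − E)/√V and rejects if |Z| > 1.96. For Wald, a comparison with no events in one arm counts as non-significant because the estimate diverges.

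| Test of the Cox model | Low | Middle | High |
|---|---|---|---|
| Score (log-rank), 20,000 runs | 14.3% | 19.4% | 22.2% |
| Wald, 6,000 runs | 1.4% | 4.0% | 11.1% |
| Likelihood ratio | 27–29% across the three | | |

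Entries are the chance that at least one of the nine is significant.

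**Step 3: why the tests differ so much.** Suppose all D events fall in one arm, with equal numbers at risk throughout. The score chi-square is (D/2)²/(D/4) = D. The likelihood-ratio chi-square is 2·D·ln 2 = 1.386·D. The threshold is 1.96² = 3.84. At D = 3 the score statistic is 3.00 (not significant) and the likelihood ratio is 4.16 (significant). The Wald statistic cannot reject at all, because the estimate diverges. With events this sparse, the choice of test drives the answer.

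**Step 4: only mortality tested.** With the score test, all-cause mortality alone gives 1.0 / 3.0 / 4.7%. Either of the two mortality endpoints gives 1.4 / 3.7 / 6.6% (6,000 runs). There is then little or no inflation with that test.

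**The case against.** The strongest reply is that 15.2 already handles this. The trial is a pilot without a statistically derived sample size, and it disclaims significance for all outcomes. Family-wise control serves confirmatory claims, and a pilot that makes none does not need it. Section 15.1 also leaves room through its unless-otherwise-stated clause and defers detail to an SAP.

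Much of this stands. It is why the remedy is to drop the claims rather than to add a multiplicity correction. But 15.2 does not withdraw the rule in 15.1 or the test in 15.4, and the clause is not used anywhere in the document.

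A reader might infer more than the documents support:
- *That all nine will certainly be tested.* Section 15.4 spells out only a mortality comparison. Its heading and its plural mention of time-to-event endpoints make wider testing a natural reading, but an inferred one.
- *That the plan carries a fixed false-positive rate, such as 15% to 27% in place of 5%.* The rate depends on assumed risks and on a test that the plan does not specify; the 27% needs an assumed correlation of 0.5. The plan never sets 5% as a family-wise target.
- *That there is no ranking at all.* Section 15.4 does single out one endpoint. The fault is that it is not identified and no testing sequence follows.

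**Conclusion.** The point holds as an internal conflict with an inexpensive remedy. Sections 15.1 and 15.4 provide for significance claims on secondary endpoints that 15.2 says the study was not designed to support. No order or alpha split is given, and the key secondary endpoint cannot be identified from 12.2.

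If all nine were tested at two-sided 0.05, the chance of at least one false significant result is about 14% to 22% with the score test, and between about 1% and 29% across the ordinary Cox tests. These figures rest on event risks the documents do not give, on 20 patients per arm and on no true difference. They show what the wording permits; they are not a fixed property of the plan. For a pilot of this size the matter is one of clarity and should not be presented as a major design flaw.

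**What to change.** 1. In 15.1 and 15.4, state that the secondary endpoints are descriptive and will be reported as event counts and effect estimates with 95% confidence intervals, with no declaration of statistical significance, in line with 15.2.
2. Either delete the reference to a key secondary endpoint in 15.4, or name it in 12.2. All-cause mortality is one candidate, since it needs no cause-of-death judgement by unblinded staff. Do not make its analysis conditional on the primary result: mortality is a safety outcome here, and gating could leave it unexamined when the primary shows no difference.

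The cost is a few sentences in the protocol or SAP, with no extra patients or data. The downside is that no secondary result can be called statistically significant, which 15.2 already concedes. This settles the conflict for the secondary endpoints only. Section 15.3 says the Cox model "will be used to test the statistical significance of differences in the composite endpoint", and that statement about the primary needs its own reconciliation with 15.2.

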15.2 Sample Size Justification and Randomization

Participants will be randomized in a 1:1 allocation ratio using a permuted block design with stratification based on the time from LVAD implant (<3 months or ≥3 months). The number of patients ≥3 months from LVAD implant will be capped at 20 participants. As this is an initial pilot study to assess safety and feasibility, we plan to enroll 40 patients.

For the primary purposes of this pilot study, each patient's data will be reviewed individually. Patients newly implanted vs previously implanted with a HM3 LVAD may be analyzed as distinct subgroups. The sample size of up to forty (40) implanted patients is based upon industry standards for early-stage studies of medical devices; the sample size was not statistically derived. This study is not designed to provide statistical significance of the outcomes. The study will provide data to be used for subsequent design and development of the phase III clinical trials. An interim report may be generated prior to completion of enrollment for regulatory or publication purposes.

15.3 Analysis of the Primary Endpoint

For the primary endpoint, a time-to-event analysis will be conducted. The Cox regression model for survival data will be used to test the statistical significance of differences in the composite endpoint (survival free of major hemocompatibility related adverse event) between the two treatment groups. Certain clinical covariates may be used in the regression model (age, sex, race, atrial fibrillation, history of stroke or bleeding prior to LVAD, early (<3 months) or late (≥3 months) after implant, laboratory parameters, hemodynamics, coagulation marker measures).

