	edoxaban, and rivaroxaban. When compared to warfarin for stroprevention in AF, apixaban is the only DOAC to demonstrate superior efficacy and lower bleeding rates. 10–12 Hypothesis: In patients with a HM3 LVAD, treatment with apixaban for 24 weeks will be non-inferior with respect to freedofrom death or hemocompatibility related adverse events (stroke, device thrombosis, bleeding, and arterial non-CNS thromboembolism), compared to treatment with warfarin.					
Study Design	This pilot study will be a prospective, randomized, controlled, open label, trial of LVAD patients with 1:1 randomization to either apixaban or warfarin. Approximately 40 patients will be randomized into the study.					
Treatment	Apixaban (Eliquis) or warfarin					
Primary Objective and Endpoint	Freedom from death or hemocompatibility related adverse events (stroke, device thrombosis, bleeding, aortic root thrombus, and arterial non-CNS thromboembolism) at 24-weeks.					
Secondary Objectives and Endpoints	 Survival free of any stroke Survival free of ischemic stroke Survival free of hemorrhagic stroke Survival free of device thrombosis Survival free of gastrointestinal bleeding Survival free of major non-gastrointestinal bleeding All-cause mortality Cardiovascular mortality 					

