4 OBJECTIVES AND ENDPOINTS

4.1 Primary Objectives

The primary objective is to evaluate the safety of apixaban as compared to warfarin in LVAD patients.

Hypothesis: In patients with a HM3 LVAD, treatment with apixaban for 24 weeks will be non-inferior with respect to freedom from death or hemocompatibility related adverse events (stroke, device thrombosis, bleeding, aortic root thrombus, and arterial non-CNS thromboembolism), compared to treatment with warfarin.

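### The primary hypothesis is non-inferiority, but the plan gives no margin or confidence-interval rule and tests only for a difference at p<0.05

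*Combined protocol and SAP*

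**What the plan says.** Section 4.1 gives the primary hypothesis: "treatment with apixaban for 24 weeks will be non-inferior with respect to freedom from death or hemocompatibility related adverse events", compared with warfarin. The executive summary (section 3) states the same non-inferiority hypothesis.

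The analysis in section 15.3 is a time-to-event comparison: "The Cox regression model for survival data will be used to test the statistical significance of differences in the composite endpoint". The threshold comes from section 15.1: "Statistical tests with a p-value <0.05 will be considered statistically significant, unless otherwise stated". Nothing different is stated for the primary endpoint. No section gives a non-inferiority margin on any scale, a confidence level or bound, or a rule for concluding non-inferiority.

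Section 15.2 calls the study a pilot of 40 patients, says "the sample size was not statistically derived" and adds: "This study is not designed to provide statistical significance of the outcomes".

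On adjustment, section 15.3 says "Certain clinical covariates may be used in the regression model" and lists candidates. One of them is time since implant (<3 or >=3 months), which sections 9.7 and 15.2 make the randomisation stratum. Section 15.4 applies a Cox significance test to mortality as well.

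Section 15.1 leaves detail to a statistical analysis plan, with this timing: "The SAP will be finalized prior to trial completion".

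**The concern.** The hypothesis and the test do not match. A non-inferiority claim requires a margin, and the confidence limit for the treatment effect must exclude it. A test of difference that returns p>=0.05 shows only that the data did not separate the arms, which is what a very small trial usually shows whatever the truth. Under the written test, only a significant result in favour of apixaban could support the hypothesis, and that is unlikely with 40 patients.

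The likeliest outcome, p>=0.05, would therefore neither support nor refute the hypothesis, and the plan does not say how to report it. No section says it would be read as non-inferiority, but none rules that reading out. The trial is open-label and the analysis plan need only be final before trial completion, so a margin or covariate set could still be settled after outcomes are known.

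What is at stake is what the pilot can conclude and pass on to phase III. Participant protection rests on the DSMB and the enrolment pauses in sections 17.1 and 17.2, which this point does not affect.

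**Working it through.** **Inputs from the documents.** 40 patients, 1:1, so about 20 per arm (15.2); 24 weeks (9.1); threshold 0.05 (15.1), taken as two-sided because no sidedness is stated. The size of 40 cannot be reproduced: no margin, power, effect size or event rate is given, and 15.2 says it was not derived.

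**Assumptions.** The documents give no 24-week composite rate and no mortality rate. I take a warfarin-arm risk of 20%, 30% or 40%, exponential event times and no censoring before 24 weeks.

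**1. How often the planned test gives p>=0.05, and how often it favours apixaban.** Log-rank simulation (the score test of the unadjusted Cox model), at least 10,000 trials per cell:

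| Warfarin risk | 20% | 30% | 40% |
|---|---|---|---|
| p>=0.05, true HR 2 | 80% | 72% | 65% |
| p>=0.05, true HR 1.5 | 91% | 88% | 85% |
| p<0.05 favouring apixaban, true HR 1 | 2-3% | 2-3% | 2-3% |
| p<0.05 favouring apixaban, true HR 0.5 | 12.5% | 16-18% | 22% |

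The Schoenfeld formula with 8, 12 and 16 events in total gives 16%, 22% and 28% power for HR 2, which is consistent. It runs slightly lower because it does not count the extra events that a true doubling produces.

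**2. Precision when the arms are truly equal.** Let d be the events per arm: 20 x 0.20 = 4, 20 x 0.30 = 6, 20 x 0.40 = 8. The standard error of the log HR is sqrt(2/d) = 0.707, 0.577, 0.500.
- Expected 95% limits for the HR, exp(±1.96 x SE): 0.25-4.0, 0.32-3.1, 0.38-2.7.
- Risk-difference half-width, 1.96 x sqrt(2p(1-p)/20): 25, 28 and 30 percentage points.

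**3. Would adding a margin help?** Take an HR margin of 2 purely as an illustration. The chance that the upper 95% limit falls below it when the arms are equal is Phi((ln 2 - 1.96 x SE)/SE):
- d = 4: Phi((0.693 - 1.386)/0.707) = Phi(-0.98) = 16%
- d = 6: Phi((0.693 - 1.132)/0.577) = Phi(-0.76) = 22%
- d = 8: Phi((0.693 - 0.980)/0.500) = Phi(-0.57) = 28%

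For 80% power at one-sided 0.025, the events needed are 4 x (1.960 + 0.842)^2 / (ln margin)^2. That gives 66 for a margin of 2.0, 191 for 1.5 and 457 for 1.3, against the 8 to 16 expected here.

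**4. Secondary: open covariate list.** Cox simulation with no treatment effect, 1,500 trials per cell, null covariates, trials without a usable fit excluded. Type I error at 30% / 40% risk:

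| Covariates | Wald | Likelihood ratio |
|---|---|---|
| 1 | 3.5% / 4.1% | 5.2% / 5.2% |
| 3 | 5.7% / 6.0% | 7.3% / 7.2% |
| 10 | 9.8% / 12.4% | 14.5% / 14.9% |

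The simulation standard error near 5% is sqrt(0.05 x 0.95/1500) = 0.56 points. One covariate does no clear harm. The three-covariate Wald figures lie within two standard errors of 5%. Ten covariates inflate the error under either test, and at 20% risk 17% of the ten-covariate trials gave no usable fit.

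**5. Secondary: mortality.** If each arm has mortality q, the chance that at least one arm has no deaths is 1 - (1 - (1-q)^20)^2, which is 89%, 59% and 23% for q = 2%, 5% and 10%. The Cox hazard ratio is then not estimable. With 0 of 20 deaths, the exact 95% upper limit is 1 - 0.025^(1/20) = 17%.

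**The case against.** The strongest reply is that section 15.2 has already conceded the point. The study is a pilot, its size was not calculated, significance is not the aim, patients' data are to be reviewed one by one, and the results are meant for designing phase III. On that reading what remains is loose wording, and showing that 40 patients are too few repeats what the protocol admits. It is true that a small pilot is not an error, and I do not ask for more patients. But the disclaimer stands beside a non-inferiority hypothesis, a significance test of the primary endpoint, a p<0.05 rule and a mortality test, all current text. A reader cannot tell which governs.

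Second, section 15.1 also commits to defining all planned analyses in advance, with coordinating-centre approval, and a later analysis plan might contain a margin. That narrows the risk. It does not remove it, because the only stated deadline is before trial completion and treatment is open-label.

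Third, 20-40% may be too low. Section 5 puts gastrointestinal bleeding alone at up to 25% in the first year, mostly in the first 3 months. Section 8.1 caps later implants at 20, so at least half of a full enrolment would be recent implants. Appendix B counts overt bleeding that merely prompts evaluation (Type 2). At 50%, 60% or 70% risk, a true doubling of the hazard still gives p>=0.05 in about 60%, 55% or 50% of trials. Replacement of apixaban patients (7.3, 14.1.8) could also take that arm above 20, but 24 against 20 moves these results by at most about 3 points. The conclusion survives both.

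Fourth, ten covariates is a worst case, and section 15.4 already plans Kaplan-Meier curves for mortality. Both are fair, and those two points are secondary.

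**Conclusion.** The concern holds. The analysis as written does not address the primary hypothesis, and section 15.2 contradicts the test without replacing it. The mismatch follows from the text and needs no assumed rates.

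The size of the consequence does rest on assumed rates. Across warfarin risks of 20% to 70% with 20 per arm, a true doubling of the hazard would give p>=0.05 in roughly 80% down to 50% of trials. At 20-40% risk, a significant result favouring apixaban would occur in at most about 22% of trials even if apixaban halved the hazard. A prespecified margin is a coherent repair in principle, but at this size it would usually fail even with equal arms, so estimation is the better choice. This should be fixed. It limits what the pilot can conclude, not the protection of participants.

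**What to change.** 1. **Sections 3 and 4.1:** restate the hypothesis as an objective to estimate the apixaban-warfarin difference in 24-week freedom from the composite. State that p>=0.05 will not be read as non-inferiority.
2. **Section 15.3:** report the hazard ratio and the 24-week Kaplan-Meier risk difference, each with a 95% confidence interval, from a primary model that accounts for the randomisation stratum (stratified Cox, or stratum as a covariate). Label any other adjusted model exploratory.
3. **Section 15.1:** state that p-values are descriptive.
4. **Section 15.4:** for mortality and rare components, add counts and 24-week risks by arm with exact confidence intervals. Do not rely on the Cox test when an arm has no events.

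**Cost.** No new patients or data. The trial gives up a formal non-inferiority claim that section 15.2 already concedes it cannot make. Changing the primary hypothesis is not an administrative change, so sections 14.1 and 18.2 require IRB approval of the amendment.
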